Patients will receive a bolus of 500 mL of 5% Albumin intravenous infusion as per the usual routine practice of the APS before the main bolus dose is injected. A preoperative level of block will be established that is appropriate for the surgery by injecting an appropriate volume of ropivacaine 0.5% or lidocaine 2% w/ epinephrine 1:200,000 (5–10 mL) into the epidural space as per the usual practice of the APS. This will be done after the routine test dosing with 3 mL of 2% lidocaine and 1:200,000 epinephrine, confirmed that intrathecal and intravascular markers are negative. If an insensate-to-cold area in the appropriate dermatomes cannot be established within 10 minutes following a 5 to 10 mL (maximum 10 mL) injection of ropivacaine 0.5%, the epidural catheter will be removed and replaced. If this process is repeated and there was still no level, it will be annotated and the patient will be removed from the study, labeled as a primary block failure, and treated appropriately by the attending anesthesiologist by either repeating the epidural block placement a third time or using other appropriate perioperative analgesia.

Research-Related Procedures - Preoperative Period:

Once consent is obtained, patients will be randomly allocated by computergenerated randomization to one of four groups. This will be a quintuple blinded prospective study. The anesthesiologist managing the intraoperative anesthesia, the anesthesiologists (APS) placing the blocks and following the patients on the floors, the research nurse taking the measurement, the surgeons, nor the patients will be aware of what combination of drugs are used for the epidural block infusion.

The three groups will consist of:

- 1. Group A (Ropivacaine 0.2% infusion; Control group)
- 2. Group B (Ropivacaine 0.2% + 2 mcg/mL epinephrine)

3. Group C (Ropivacaine 0.2% + 5 mcg/mL epinephrine)

The pharmacists will make up and supply test drugs for groups A, B and C and provide them labeled to the block area drug dispenser as "A, B, or C test solutions" without specifically identifying the content.

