Immediately following the establishment of an appropriate level for the planned surgery, an infusion of the test drug will be initiated at 4 to 8 mL per hour with a 4- to 8-mL patient-initiated bolus at a lockout interval of 1 hour – typically 8 mL per hour for major abdominal or thoracic surgery and thoracic epidural placement and 4 mL per hour for hip arthroplasty and lumbar epidural. Once established as effective for the clinical situation, this infusion will be left unchanged throughout the surgery and postoperative period. If clinically indicated, and the infusion rate is changed to below the limits of 4 – 8 mL per hour, this indicates the end of the need for the epidural infusion or otherwise untreatable hypotension.

Standard of Care - Intraoperative and Postoperative Periods:

Intraoperative and postoperative fluid management will be at the discretion of the anesthesia and primary teams.

Preoperative sedation will be a maximum of 5 mg of midazolam by intravenous injection (IV) and alfentanil 2000 mcg IV. Monitors include: EKG, non-invasive blood pressure, ETCO2, pulse oximeter, arterial line with Flow-Track (if indicated and appropriate per intra- or postoperative operative anesthesiologist), peripheral intravenous or central venous line as deemed appropriate by the attending intra- or postoperative operative anesthesia and mode of anesthesia (maintenance, fluid management, intraoperative analgesia, muscle relaxation, etc., are at the discretion of the attending intraoperative anesthesiologists.

If hypotension (see definition below) is encountered intraoperatively, the attending anesthesiologist will start a vasoactive or positive inotropic medication as indicated by the patient's medical requirements.

Research-Related Procedures – Intraoperative:

- Anesthesiologists will be encouraged to use alpha agonists if the other causes of hypotension are excluded and lumbar epidural is judged to be a contributory cause of the hypotension; and epinephrine, dobutamine, or dopamine (or indirect inotropic agents such as ephedrine) if thoracic epidural is judged to be the cause of the hypotension and the other causes of hypotension such as hypovolemia have been ruled out.

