Primary measurements:

Include the average invasively or non-invasively measured SBP, diastolic blood pressure (DBP), MAP, arterial blood oxygen saturation (SaO2), heart rate, respiratory rate, and pain by the visual analog pain score (VAS) on the "Defense and Veterans Pain Rating Scale" (DVPRS) measured over the following set periods:

Preoperative period

Primary measurements every 3 to 5 minutes and at indicated time points:

- I. Before the bolus epidural is injected.
- II. After the epidural bolus is injected but before anesthesia is induced.

Intraoperative period

Primary measurements every 3 to 5 minutes

Postoperative period

I. Primary measurements in the recovery room (if appropriate) every 15 minutes

II. Primary measurements following transfer to the floor every 4-6 hours if within normal limits, but every hour if needed for closer observation in case of possible abnormality for as long as the epidural analgesic blocks are continued, but at least every 8 hours after discharge from the PACU.

Secondary measurements:

[figure not shown]
- III. Spread of block per spinal root segment as tested by sensitivity to cold recorded every hour postoperatively and every 8 hours for the subsequent 72 hours after discharge from the PACU.
- IV. Ambulation on the first day after surgery (POD 1), POD 2 and 3, will be recorded per physical therapy protocol and distance ambulated per 24hour period will also be recorded. Physical Therapy information will be gathered to test motor effect on lumbar epidurals.
- V. Opioid usage data will be recorded and converted to morphine equivalents and averaged for POD 0, 1, 2, and 3 per group.
- VI. Side effects such as pruritus, nausea/vomiting, and respiratory depression (defined as respiratory rate less than 10 breaths per minute of oxygen saturation more than 7 points lower that the patients preoperative value on room air) will be recorded and managed as deemed appropriate by the attending physician.
- VII. 24 hour I/O for the first 72 hours to assess fluid balance, length of stay, and amount of days before return to PO status.

Data analysis plan

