All data will be entered securely using the online database or Red Cap. To assess potential dose-response effects on changes in continuously measured primary outcomes, repeated measures mixed modeling analyses will be used. This type of analysis can assess the main effects of time (i.e., change) and group (i.e., epinephrine dose; coded as an ordinal variable) on the outcomes. Mixed models are the preferred approach to analyze data with repeated measures; these models can account for correlation among repeated measurements, flexible time effects, and can handle missing data. Additionally, this model can estimate time × group interactions. If this interaction is statistically significant, that provides evidence that the changes in outcomes are different depending on the dose of epinephrine that a patient received. Logistic regression models will be used to assess the relationship between epinephrine dose and incidence of hypotension (SBP < 20% or MAP < 55 mmHg) and other categorical outcome variables. A P value of <0.05 was considered statistically significant for all statistical tests. All analyses were conducted in JMP Pro 11.0 (SAS Institute, Cary, NC).

Sample size determination

At 80% power (alpha = 0.05), a sample of n=200 (50 per group) will be able to detect 26% differences in incidence of categorical outcomes, and an effect size of Cohen's f = 0.24 for group mean differences and effect size of Cohen's f = 0.09 for group differences mean change over time. Figure 1 depicts how these effect sizes will translate to the outcomes, with assumed standard deviations in outcomes ranging from 5 to 25. For example, assuming MAP has an SD = 10, the present study will be able to detect mean differences of 5 mmHg across groups and group differences of 3 mmHg for mean change over time.

ADMINISTRATIVE RESPONSIBILITIES:

Study Resources: The principal investigator will oversee the data collection, data analysis and will maintain the records in confidence. Should any evidence suggest that the study protocol require modification, the PI will notify the IRB in a timely manner for review and approval. Each subject will be identified by number, not by name, on all data forms. To protect confidentiality, all data will be numerically coded and information linking the numeric codes to individual participant's names will be kept in a locked file in the PI's office.

7. Possible Discomforts and Risks:

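### Thoracic and lumbar epidurals are enrolled together, but catheter level is neither a named stratification factor nor a term in the stated models, which costs precision and leaves chance imbalance uncontrolled

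*Combined protocol and SAP*

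**What the plan says.** All references are to the combined protocol and SAP, section 6 (Research Plan), unless stated.

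- **Population.** The inclusion criteria admit thoracic, abdominal, urological and orthopaedic surgery with either a thoracic or a lumbar block. The expected mix is not given.
- **Infusion.** Under Research-Related Procedures - Preoperative Period, the permitted range is 4 to 8 mL/h plus a 4 to 8 mL patient-initiated bolus with a one-hour lockout. The rate is "typically 8 mL per hour for major abdominal or thoracic surgery and thoracic epidural placement and 4 mL per hour for hip arthroplasty and lumbar" epidurals.
- **Level treated as relevant.** The intraoperative procedures encourage different classes of vasoactive drug according to whether a lumbar or a thoracic epidural is judged responsible for hypotension. Secondary measurements, item IV, adds: "Physical Therapy information will be gathered to test motor effect on lumbar epidurals".
- **Randomisation.** "patients will be randomly allocated by computergenerated randomization to one of four groups". No stratification factor is named.
- **Analysis.** The mixed model for the continuous primary outcomes has time, "group (i.e., epinephrine dose; coded as an ordinal variable") and their interaction. The logistic model relates hypotension and other categorical outcomes to epinephrine dose. No term for level, surgery or infusion rate is mentioned, and no analysis by level is planned.
- **Sample size.** "At 80% power (alpha = 0.05), a sample of n=200 (50 per group") is said to detect "an effect size of Cohen's f = 0.24 for group mean differences".

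**The concern.** Catheter level is known before the infusion starts and can be specified at randomisation as the planned level. It goes with the type of surgery, the typical infusion rate and, in the protocol's own account, the handling of hypotension. It is therefore a strong candidate for a prognostic factor: segments blocked, distance walked after hip arthroplasty rather than thoracic surgery, and the risk of hypotension may all differ by level.

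Leaving such a factor out of both design and model has three consequences.

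1. Between-level variation stays in the error term.
2. The arms may differ in their level mix by chance, and nothing in the design or analysis corrects for it.
3. The result is harder to interpret. The same concentration gives different hourly epinephrine at the two levels, and the lumbar motor question has no lumbar analysis attached to it.

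**Working it through.** **1. The plan's own figures.** The inputs are alpha 0.05 (taken as two-sided), 80% power, N = 200 and 50 per group, which means four groups.

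- *Group means.* One-way ANOVA, noncentrality = N x f² = 200 x 0.24² = 11.52 on 3 and 196 df. Power is 81.5%, and the f that gives exactly 80% is 0.236. The stated 0.24 reproduces.
- *Incidence.* A 26-point difference at 50 per arm gives 80.5% power for 45% versus 19%, and 77.7% for 50% versus 24%. It reproduces for control rates in the mid-40s; the plan states no control rate.
- *Change over time.* The stated f = 0.09 is matched by, for example, six time points with correlation 0.5 (0.089). The plan gives neither input.

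**2. Chance imbalance in level.** For a thoracic share p and n per arm, the SD of the between-arm difference in share is sqrt(2p(1-p)/n).

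- p = 0.5, n = 50: sqrt(2 x 0.25/50) = 0.10, so 10 points, with a 95% range of about ±20.
- p = 0.3, n = 50: sqrt(2 x 0.21/50) = 0.092.
- By simulation at these shares, an imbalance of at least 10 points between two arms has probability 33-37%, and of at least 20 points 4-6%.

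If the risk of hypotension differs by 20 to 40 points between levels (assumption), a 10-point imbalance moves an arm difference by 0.10 x 20 to 0.10 x 40 = 2 to 4 points. A 20-point imbalance moves it by 4 to 8. The stated detectable difference is 26.

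**3. Precision.** Suppose outcomes differ between levels by δ within-level SDs, and f = 0.24 is on the within-level SD. Omitting level multiplies the variance by 1 + p(1-p)δ², so the effective f is 0.24 / sqrt(1 + p(1-p)δ²).

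| δ (assumed) | Variance factor, p = 0.3 / 0.5 | Power, p = 0.3 / 0.5 |
|---|---|---|
| 0 | 1 / 1 | 81.5% |
| 0.5 | 1.05 / 1.06 | 79.3% / 78.9% |
| 1 | 1.21 / 1.25 | 72.9% / 71.3% |
| 2 | 1.84 / 2.00 | 52.8% / 49.1% |

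The procedures list three groups where the sample size has four. That conflict is a separate matter. With three groups and N = 200 the same calculation starts at 86.4% and falls to 84-85%, 77-79% and 56-60%, so the pattern is unchanged.

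**4. Delivered epinephrine** (mcg/h = concentration x volume per hour).

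| | Lumbar, 4 mL/h | Thoracic, 8 mL/h |
|---|---|---|
| Group B, 2 mcg/mL | 2 x 4 = 8 | 2 x 8 = 16 |
| Group C, 5 mcg/mL | 5 x 4 = 20 | 5 x 8 = 40 |

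At basal rates B spans 8-16 and C spans 20-40, with no overlap. Adding 0 to 8 mL/h of boluses gives B 2 x (4 to 16) = 8-32 and C 5 x (4 to 16) = 20-80. The ranges then share 20-32. A Group B patient enters that range at 10 mL/h in total (20/2), which is 2 mL/h of boluses on top of 8. A Group C patient is in it only up to 6.4 mL/h in total (32/5).

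**5. Analysis within one level.** At an assumed 25 per arm per level, power for 45% versus 19% falls from 80.5% to 50.4%. The detectable difference from a 50% control rate rises from 26.7 to 36.1 points.

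**The case against.** Much of the case on the other side stands, and it limits the point.

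- **Bias.** A reader might infer that pooling biases the comparison. It does not in expectation, because concentration is randomised within a mixed population. Section 5 asks for the best concentration, so coding the arms by concentration answers the stated question.
- **Overlap.** A reader might infer that the 8 and 4 mL/h rates make the dose groups overlap. They do not. Overlap needs a Group B patient who uses boluses and a Group C patient who uses few or none, and bolus frequency is not given. At equal volume, C always receives 2.5 times B.
- **Different measures.** Hypotension has one definition at both levels, relative to the patient's own baseline or an absolute MAP limit. The issue there is different baseline risk and possible effect modification, not two different endpoints.
- **Silence is not evidence.** The allocation is described only as computer-generated; to call it simple randomisation would be an inference. No model is stated for continuous secondary outcomes, so unadjusted pooling of block spread and distance walked is likewise inferred.
- **Delivered volume.** The documents do not show that it goes unrecorded. Section 7 lists amounts and times of drug administration among the data, and the activity table lists pain service records through POD 3. Bolus volume is not named as a measurement and enters no analysis.
- **Size.** At half an SD between levels the loss is only 2 to 3 points of power. If the SDs in the sample-size section already include between-level variation, adjustment is a gain forgone rather than a shortfall. A constant level difference also does not affect the time-by-group test; for that test, level matters only if it alters the course over time.

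None of this gives a reason to leave level out of the design and the models.

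**Conclusion.** The point holds as one of precision, chance imbalance and interpretability. The documents enrol both levels, treat level as clinically relevant, and name it neither in the randomisation nor in the stated models.

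The loss runs from negligible to serious: from 81.5% power to about 79%, 71-73% or 49-53% for level differences of 0.5, 1 or 2 within-level SDs. A 10-point imbalance in level between two arms would arise by chance about one time in three. These figures rest on an assumed thoracic share of 30-50%, assumed outcome differences, and f expressed on the within-level SD; the documents supply none of these. The twofold difference in basal delivery at a given concentration follows directly from the protocol's typical rates.

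The documents do not support a conclusion that the trial is biased, that Groups B and C overlap at basal rates, or that hypotension is a different measure at each level. This is an inexpensive improvement that should be made, not a flaw that invalidates the design.

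**What to change.** 1. Stratify the computer-generated randomisation by planned catheter level (thoracic or lumbar).
2. Include level as a factor in the mixed and logistic models and in the analyses of block spread and ambulation, which need a stated model. If the time course is expected to differ by level, consider a level-by-time term in the mixed model.
3. Keep the pooled, level-adjusted comparison of assigned concentrations as the main analysis.
4. Report results by level, including ambulation in lumbar patients for the stated motor question, and label them descriptive or exploratory because power within one level is low.
5. As supporting information, summarise delivered epinephrine (mcg/h, boluses included) by arm and level from the drug-administration records, and confirm that those records capture bolus volume.

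The cost is one stratification factor and one model term, plus the by-level tables. In the logistic model the odds ratio becomes conditional on level, which the report should say. No dose or rate change is proposed.

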Regional anesthesia - The risks of regional anesthesia include, but are not limited to low blood pressure, allergic reaction to drugs, obstruction or cessation of breathing, headache, paralysis, nerve injury, bleeding, blood clots, infection or meningitis, falls after surgery, drug reactions (including rash, shock, and cardiac/respiratory arrest), stroke or brain injury, heart failure or heart attack, and death. The epidural would be immediately turned off if the patient were to have unwanted side effects such as uncontrolled increase in heart rate or blood pressure, arrhythmias, anxiety, or unwanted clinical symptoms that could be attributed to the epinephrine dose in the epidural. The pharmacy would immediately be contacted to determine the epinephrine dose in the patient's epidural so that clinical treatment be tailored appropriately.

The PI will oversee the data collection, data analysis, and will maintain the records in confidence. The data collected will be stored in a secure, password protected database with strong encryption, on a computer server, accessible only by the study team. Any additional digital data files from the study will be de-identified and stored on a password protected laptop computer. Hence, encryption will be required. All paper records will be stored in locked file cabinet in the PI's locked office. The patient consent forms will be the only documentation with PHI. The results collected and calculated by the laptop software will be non-PHI data including the patient demographics, administration amounts of drugs, the time of those administrations, and the post-operative times to emergence and the occurrence of respiratory depression.

8. Possible Benefits:

It has been proven beyond doubt that epinephrine, when added to ropivacaine 0.2% and used for epidural analgesia by infusion, is safe and may even improve spinal cord blood flow and the analgesic effects of ropivacaine.⁷ Because of this, the possible benefit to the participant is to improve the effects of the epidural anesthesia and to reduce the possible sympathetic side effects.

9. Conflict of Interest:

None of the investigators have a conflict of interest.

References

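### Treating intraoperative hypotension attenuates the averaged blood pressure outcomes, and vasoactive drug use is not among the visible listed outcomes

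*Combined protocol and SAP*

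**What the plan says.** All places are in section 6 (Research Plan) of the combined protocol and SAP unless stated.

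- **Trigger.** Standard of Care – Intraoperative and Postoperative Periods: when hypotension is met during surgery, "the attending anesthesiologist will start a vasoactive or positive inotropic medication", according to the patient's needs. This applies in every arm.
- **Agents.** Research-Related Procedures – Intraoperative encourages alpha agonists where a lumbar epidural contributes, "and epinephrine, dobutamine, or dopamine (or indirect inotropic agents such as ephedrine) if thoracic epidural is judged to be the cause". Epinephrine is also the additive under test.
- **Outcome.** Primary measurements: "Include the average invasively or non-invasively measured SBP, diastolic blood pressure (DBP), MAP", with heart rate and other variables, over set periods. For the intraoperative period the schedule is "Primary measurements every 3 to 5 minutes".
- **Analysis.** The data analysis plan uses repeated-measures mixed models for the continuous outcomes and logistic regression for the incidence of hypotension. It has no rule for readings taken on a vasoactive drug.
- **Drug use as an outcome.** Opioid use is the only drug use in the visible secondary list, and the rescue drugs itemised in the protocol are analgesics. A figure at the head of that list is not shown. The numbering there starts at III and seems to continue postoperative items I and II, so a vasoactive outcome in the figure is unlikely but cannot be ruled out.
- **Source data.** The activity table collects intraoperative records. Section 7 says stored data include "administration amounts of drugs, the time of those administrations", without naming vasoactive drugs.

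**The concern.** The treatment is triggered by the outcome. A patient whose pressure falls is given a drug that raises it, and the raised readings are averaged with the rest. If epidural epinephrine prevents some hypotension, the control arm receives more of this treatment, so its average is lifted more and the arms move closer together. Heart rate readings are affected too, though the documents do not settle in which direction.

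Two things are at stake. The mean-pressure comparison answers a different question from the one a reader will assume: it shows pressure with rescue, not what the epidural solution alone does. And less need for vasoactive support, which is direct evidence on specific aim 1a (preventing hypotension), is not a listed comparison.

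**Working it through.** **1. The plan's own figure.** Sample size determination gives 80% power, alpha 0.05, N = 200 (50 per group) and Cohen's f = 0.24. For a one-way ANOVA the noncentrality is N × f² = 200 × 0.0576 = 11.52. With four groups power is 0.815, so the figure reproduces. With SD 10, 2 × 0.24 × 10 = 4.8, which matches the stated 5 mmHg. With the three listed arms of 50, power is 0.743; the mismatch between three and four groups is a separate point. The calculation makes no allowance for rescue.

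**2. Attenuation with the SD held fixed.** Take a pairwise comparison, two-sided 0.05, 50 per arm, SD 10. The standard error is 10 × √(2/50) = 2 mmHg, and power = Φ(difference/2 − 1.96).

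| Difference left (mmHg) | Lost from 5 | Power |
|---|---|---|
| 5 | 0% | Φ(0.54) = 0.71 |
| 4 | 20% | Φ(0.04) = 0.52 |
| 3 | 40% | Φ(−0.46) = 0.32 |
| 2 | 60% | Φ(−0.96) = 0.17 |

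This is pessimistic, because rescue also pulls up the lowest patients and so narrows the spread.

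**3. Simulation that lets the spread change.** The documents supply 50 per arm, the 5 mmHg difference, the reading interval and the 20% threshold. Everything else is assumed:

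- two arms; baseline MAP 90; mean fall 12 in control and 12 − 5 = 7 with epinephrine
- between-patient SD 8.7, within-patient SD 3
- 36 readings (3 hours at 5-minute intervals)
- event: any MAP reading below 0.8 × 90 = 72 (the 20% criterion, which the plan applies to SBP, is applied here to MAP)
- after the first event, all later readings rise by a fraction r of the gap between the patient's own mean and 0.9 × 90 = 81
- t-test on patient averages, chi-square test on incidence, 1,500 trials per row

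| r | Mean difference (mmHg) | Power, means | Incidence, control vs epinephrine | Power, incidence |
|---|---|---|---|---|
| 0% | 5.0 | 0.81 | 52% vs 30% | 0.61 |
| 25% | 4.3 | 0.81 | 51% vs 30% | 0.60 |
| 50% | 3.8 | 0.81 | 52% vs 30% | 0.63 |
| 75% | 3.2 | 0.75 | 51% vs 30% | 0.60 |
| 100% | 2.6 | 0.67 | 52% vs 29% | 0.62 |

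The difference shrinks by (5 − 4.3)/5 = 14% to (5 − 2.6)/5 = 48%. Power falls less than the difference does, because the SD shrinks as well. Incidence does not move, because the qualifying reading comes before the drug.

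**4. Sensitivity to the restoration target.** If rescue lifts patients toward the full baseline of 90 instead of 81, the difference is about 2.9 mmHg at 50% restoration. It falls below 1 mmHg only with complete and permanent restoration.

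**The case against.** The strongest reply is that prevention is tested by the incidence analysis, not by mean pressure. The drug starts once hypotension is met, so the triggering reading is normally already recorded. This largely stands. A reader might infer that a real preventive effect is masked altogether; the documents do not support that, because the planned logistic regression can still see it. The protection has limits. The plan does not say whether incidence comes from any single reading or from period averages, and averages would be attenuated too. A drug given before a qualifying reading counts as no event, although the documents do not show how often that would happen. A brief dip also scores the same as prolonged support.

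A reader might also infer that nearly all the difference disappears. For example, 40% against 20% hypotensive with a 20 mmHg fall gives 0.2 × 20 = 4 mmHg untreated. If rescued patients stay low for only 10–20% of the period, 0.4–0.8 mmHg is left. That result comes from the assumed share of time spent low and from assuming no difference in other patients. Its untreated 4 mmHg is already below the 5 mmHg that the plan says it can detect.

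Two further replies are fair. The quoted trigger is intraoperative, and no matching postoperative vasoactive rule is stated, so the point does not extend to the ward readings. And comparing pressure as observed, rescue included, is a legitimate treatment-policy question; the defect is that the plan does not state this choice.

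**Conclusion.** The point holds as attenuation of the averaged intraoperative pressures, together with an omitted outcome. The direction follows from the protocol's own rules, provided that rescue raises pressure and is used more in the arm with more hypotension. The size is illustrative: a true 5 mmHg difference falls to about 4.3–2.6 mmHg and power lies between 0.81 and 0.67, given restoration toward 90% of baseline and the other assumptions above. Fuller restoration would cost more. The incidence contrast largely survives if any single reading counts. In the simulation, however, it is 52 − 30 = 22 points, under the 26 points the plan is sized for, with power of only 0.60–0.63. A comparison of vasoactive need would therefore add information on aim 1a. This is a cheap and worthwhile improvement; it does not invalidate the design.

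**What to change.** 1. **Secondary measurements:** add any intraoperative vasoactive or inotropic use, and cumulative dose, as outcomes compared between arms. Take agent, dose and time from the intraoperative records.
2. **Data analysis plan, incidence:** define hypotension incidence from any single qualifying reading.
3. **Data analysis plan, composite:** add a logistic-model outcome of a qualifying reading or the start of a vasoactive or inotropic drug for low pressure.
4. **Data analysis plan, mixed model:** state that the mean-pressure comparison follows a treatment policy, includes readings on rescue, and is read alongside the vasoactive outcome.

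Replacing on-drug readings with the last value before rescue is debatable and is not needed.

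The cost is wording plus extraction from records the study already collects, although no vasoactive variable is yet defined. Some drug starts will be unrelated to the epidural, since anesthetic and fluid management are discretionary. Under the planned blinding that should add mainly noise; its amount cannot be estimated from the documents. Clinical rescue rules do not change.
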